# 2.15 Data Analysis

All data will be analysed using The jamovi project (2022) (Version 2.3). Descriptive statistics (frequency and percentage; mean and standard deviation) will be used to describe the socio-demographic characteristics of the participants.

Categorical variables, expressed as numbers and percentages, are compared by the Chi-square test. Continuous variables will be tested for normality using One-Sample Kolmogorov-Smirnov Test and compared using independent t-test for normally distributed data and the Mann-Whitney U test for non-normally distributed data. Data with normal distribution are reported as mean (standard deviation, SD), while non-normally distributed variables are reported as median (interquartile range, IQR).

The predictors associated with medication discrepancies will first be analysed using univariable logistic regression. The variables with p-value <0.1 by univariable analysis will be included in the multivariable logistic regression model. All statistical tests are two-tailed and p<0.05 is set to be statistically significant.

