Specific objective 4: To identify the predictors associated with medication discrepancies in the first prescription upon transition of care from hospitals to primary health clinics.

H4a

There is a significant association between age of patient, number of comorbidities, number of medications, type of medication (ATC categorization), experienced of prescriber (category of prescriber) and medication discrepancy in the first prescription upon transition of care from hospitals to primary health clinics.

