#### 2.4.3 Withdrawal criteria

Patients readmitted to hospitals before the first review at the health clinic shall be withdrawn from the study. Patients can choose to withdraw at any time. Withdrawn patients will not be replaced.

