### 2.5 Sample Size Calculation

This study aims to compare the prevalence of medication discrepancies in the first prescription upon transition of care from hospitals to primary health clinics between MedBook Portal and standard care. Hence, a two-tailed z-test of proportion between two groups with 80% power and a 5% of level significance will be used (10). The prevalence of medication discrepancies upon discharge reported in a previous study is 49% (8). We estimate the reduction of medication discrepancies via implementation of MedBook is 15%. Thus, a sample size of 322 subjects, 161 subjects in each group, is sufficient to detect a clinically importance difference of 15% between groups. However, with the estimation of a 20% loss to follow up, a total of 386 subjects will be recruited.

In addition, this study also aims to ascertain the prevalence of medication discrepancies and type of medication discrepancies in discharge prescription and in the first prescription upon transition of care from hospitals to primary health clinics. Sample size is calculated by using the following formula (11):

$$n = \frac{Z^2 P(1-P)}{d^2}$$

where n = sample size,

Z = Z statistic for a level of confidence,

P = expected prevalence or proportion

d = precision

By determining the Z = 1.96 for 95% CI and d = 0.05, the minimum sample size is 384. Based on the above sample size calculation, a total of 386 patients will be recruited. The sample size allocation for each hospital is determined on a pro-rata basis based on the total bed numbers in general medical wards and Bed Occupancy Rate (Table 2.4).

**Table 2.4:** Sample Size Allocation Of Each Hospitals

Public Major	Wards	Total	Bed	Sample
Hospitals		Bed	Occupancy	Size
		Numbers	Rate (%)	Allocation
Sarawak General	Male General Ward	48	114.4	144
Hospital	Female General Ward	48	102.0	
Sibu Hospital	Male General Ward 1	36	62.2	106
	Male General Ward 2	36	73.4	
	Female General Ward	32	83.5	
Miri Hospital	Male General Ward	29	114.1	72
	Female General Ward	30	62.8	
Sarikei Hospital	Male General Ward	35	82.4	64
	Female General Ward	35	50.2	
Total	-	329	-	386

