#### 2.7 Data and Instruments

#### 2.7.1 Data Collection Form

Medication discrepancies detected will be categorised according to the following groupings, discrepant dose, discrepant frequency, polypharmacy, drug omission, drug addition and inappropriate drug. Other data that will be collected include age, gender, number of medications, type of medication based on Anatomical Therapeutic Chemical (ATC) categorisation in Drug Formulary Ministry of Health Malaysia, comorbidities, and category of prescriber.

There are two electronic data collection forms using Google Form for data entry. The first data collection form (Appendix A) is administered by pharmacist at hospital before allocation. The second data collection form (Appendix B) is to be administered by pharmacist at the health clinic.

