# 2.9 Medication Reconciliation Upon Hospital Discharge

Medications in the discharge prescription will be considered as the primary source of reference for discharge reconciliation, as this is the list of medications that the pharmacy will refer to for medication preparation and eventually will be given to the patients upon discharge. Study pharmacists will conduct discharge medication reconciliation before randomization. Discharge medication reconciliation will be carried out by comparing the medications in the discharge prescription against the medications in the medication history assessment form (pre-admission medications) and inpatient medication charts (medications started during admission) to detect medication discrepancies before discharge medications preparation. If any differences are detected, study pharmacists will confirm with the doctor to decide intentional or unintentional medication discrepancies-any amendment to be documented on the discharge prescription.

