#### 2.13 Data Collection

The prevalence of medication discrepancies during discharge is collected through medication reconciliation by the study pharmacist at the hospital using the electronic data collection form. In addition, the type of medication discrepancies and predictors associated with medication discrepancies will be collected simultaneously using the first data collection form (Appendix A) by the study pharmacist at a hospital before allocation.

To compare the prevalence of medication discrepancies in the first prescription upon transition of care from hospitals to primary health clinics between the MedBook Portal and standard care,

data collection on the number of medication discrepancies will be carried out during the first follow-up at the health clinic after the hospital discharge. A pharmacist will administer the second data collection form (Appendix B) at the health clinic.

Throughout the study, there is only one follow-up visit at the health clinic, the first after hospital discharge. However, the time frame between the discharge date and the appointment date for the first follow-up at the health clinic varies from days to weeks depending on the duration determined by the hospital. Thus, the expected duration of subject participation would range from one week to two months.

To reduce loss to follow-up, the study pharmacist shall contact the patient via WhatsApp or phone call to remind the patient of the follow-up date at the health clinic. The schedule of enrolment, interventions and assessments of the study are presented in Table 2.5. The study flow chart is illustrated in Figure 2.5.

Table 2.5: Schedule of Enrolment, Interventions and Assessments

Timepoint	Study Period			
	Enrolment	Allocation	Post-	Close-out
			allocation	
	-tı	0	1 st Primary	
			Health Clinic	
			Follow Up	
ENROLMENT:				
Eligibility screen	X			
Participant	X			
Information Sheet				
Informed consent	X			
Allocation		X		
INTERVENTIONS:				
MedBook Portal		X	X	
ASSESSMENTS:				
Prevalence of	X		X	
medication				
discrepancies				
Predictors of	X		X	
medication				
discrepancies				

[figure not shown]

Figure 2.5: Study Flow Chart

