# **APPENDICES**

**Appendix A:** Data Collection Form to be administered by Pharmacist at Hospital (https://forms.gle/wZrjjTpgLtHM8cb59)

Refer to * Mark only one oval.	KK Sentosa  KK Batu Kawa  KK Samarahan  KK Jalan Oya  KK Lanang  KK KI Lanang  KK Sibu Jaya  KK Miri  KK Tudan  KK Bintangor	Comorbidities as per case note (Please list down refer) *	Number of Medication *	Category of prescriber *  Mark only one oval.  House Officer  Medical Officer  Consultant/ Specialist
5		ø	7.	∞i

 
Type of Medication Discrepancies * Mark only one oval.
 
	Discrepant dose     Discrepant frequency     Polypharmacy	Drug Omission	Drug Addition Inappropriate Drug	15. Any other Unintentional Medication Discrepancies? *	Mark only one oval.	○ Yes	oN (		Drug #3	16. Drug Name with Unintentional Medication Discrepancy *		
 
Type of Medication Discrepancies *
 
	Mark only one oval.	Oiscrepant dose	Discrepant frequency	— Polypharmacy	Drug Omission	Drug Addition	Inappropriate Drug	

 
Any other Unintentional Medication Discrepancies? * Mark only one oval.
 
	○ Yes	Drug #1	
 
Drug Name with Unintentional Medication Discrepancy *
 
	11. Type of Medication Discrepancies *	Mark only one oval.	Oiscrepant dose	Discrepant frequency	O Polypharmacy	Drug Omission	Drug Addition	Inappropriate Drug	12. Any other Unintentional Medication Discrepancies? *	Mark only one oval.	○ Yes	ONO		Oning #3	7# ford	
 
Drug Name with Unintentional Medication Discrepancy *
 
	

 
Type of Medication Discrepancies *
 
Mark only one oval.
 
	Discrepant dose     Discrepant frequency     Polypharmacy	Drug Omission	Drug Addition Inappropriate Drug	24. Any other Unintentional Medication Discrepancies? *	Mark only one oval.	Yes	on O		Drug #6	25. Drug Name with Unintentional Medication Discrepancy *		26. Type of Medication Discrepancies *	Mark only one oval.	Oiscrepant dose	Discrepant frequency	— Polypharmacy	Drug Omission Drug Addition	Inappropriate Drug	

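### The primary arm comparison is valid but unadjusted and has no planned confidence interval; pre-allocation predictors the trial already records could sharpen it modestly

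*Combined protocol and SAP*

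**What the plan says.** Section 2.14 defines the primary outcome as the percentage of first clinic prescriptions with discrepancies and says that the arms will be compared. It names no effect measure. Section 2.15 does not mention the primary outcome by name; the rule that applies to it is "Categorical variables, expressed as numbers and percentages, are compared by the Chi-square test". Section 2.5 states that "a two-tailed z-test of proportion between two groups with 80% power and a 5% of level significance will be used". The only 95% CI in the plan, also in 2.5, sizes a single prevalence.

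On baseline data, section 2.7.1 says: "The first data collection form (Appendix A) is administered by pharmacist at hospital before allocation". Section 2.13 agrees that the predictors "will be collected simultaneously using the first data collection form (Appendix A) by the study pharmacist at a hospital before allocation". Appendix A has fields for referral clinic, comorbidities, prescriber category and "Number of Medication". The recruiting hospital is known at enrolment.

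H4a, which concerns the first clinic prescription and so the primary outcome, reads in part: "There is a significant association between age of patient, number of comorbidities, number of medications". Section 2.15 uses these variables in logistic regression for the predictor objectives, after a univariable screen at p<0.1. Study arm is not among the five predictors that H4a lists.

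**The concern.** The trial expects certain patient characteristics to drive its primary outcome and records them before randomisation, but does not use them where the main question is answered. Adjusting for prognostic baseline variables fixed in advance usually narrows the interval for a treatment effect without more patients. If no adjusted comparison is pre-specified, any adjusted arm effect that appears later will have been chosen after the data were seen.

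The missing interval is a smaller gap. H1a is quantitative (15 points lower with MedBook) and 2.5 calls 15 points clinically important. A p-value beside two percentages does not show directly which differences the data support or exclude.

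**Working it through.** **Inputs.** From 2.5 and H1a: control rate 49%, difference 15 points (so 34%), two-sided 5%, 80% power, 161 per arm, 386 recruited, 20% loss. From 2.10: 1:1 allocation. From Table 2.4: hospital shares 144/106/72/64. Predictor strength is not in the documents and is varied as an assumption.

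**1. The plan's own figure.** The pooled formula is n per arm = [1.96√(2p̄q̄) + 0.842√(p₀q₀+p₁q₁)]² / 0.15², with p̄ = 0.415, 2p̄q̄ = 0.48555 and p₀q₀+p₁q₁ = 0.2499 + 0.2244 = 0.4743. It gives 168.2, so 169 per arm. The stated 161 is not reproduced; power at 161 is 78.2%. That is a separate matter and nothing below depends on it.

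**2. One test or two?** Take 75/154 against 53/155, close to 49% and 34%. The uncorrected chi-square is 6.7007 and z² is 6.7007 (p = 0.0096). Sections 2.5 and 2.15 therefore describe the same test.

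**3. Unadjusted baseline.** Evaluable patients: 386 × 0.8 = 308.8, about 309, or 154.4 per arm.
- SE under the null: √(0.48555/154.4) = 0.05608
- SE under the alternative: √(0.4743/154.4) = 0.05542
- Power: Φ[(0.15 − 1.96 × 0.05608)/0.05542] = Φ(0.723) = 76.5%
- 95% half-width: 1.96 × 0.05542 = 0.109. An observed 15-point difference would have a CI of about 4 to 26 points.

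**4. Effect of adjustment.** Let v be the variance of the adjusted (standardised) risk difference divided by that of the unadjusted one. Both SEs are multiplied by √v, so power = Φ[(0.15/√v − 0.1099)/0.05542]. Values of v come from simulation: 60,000 trials per scenario, n = 309, four hospitals in the Table 2.4 proportions with assumed log-odds shifts of −0.2/+0.2/+0.1/−0.1 (0 in the useless case), one standard normal covariate, and marginal rates held at 49% and 34%.

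| Assumed OR per SD | v | Power | Change (before rounding) | Half-width (points) |
|---|---|---|---|---|
| 1.0 (useless) | 1.013 | 76.0% | −0.5 | 10.9 |
| 1.2 | 0.997 | 76.7% | +0.1 | 10.8 |
| 1.5 | 0.969 | 77.8% | +1.3 | 10.7 |
| 1.8 | 0.936 | 79.2% | +2.7 | 10.5 |
| 2.2 | 0.890 | 81.2% | +4.7 | 10.2 |

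Example, OR 1.5: 0.15/√0.969 = 0.1524; (0.1524 − 0.1099)/0.05542 = 0.766; Φ = 77.8%. In patients, 309/0.969 = 319, about 10 more. Reaching 80% by adjustment alone needs v of about 0.92, which lies between OR 1.8 and OR 2.2.

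Simulated power for the logistic arm coefficient, against chi-square, was 76.3 v 76.7, 76.9 v 76.5, 78.1 v 76.7, 79.7 v 77.1 and 81.3 v 76.7%, which agrees. Type I error was 5.1 to 5.5% for chi-square and 5.0 to 5.4% for the adjusted analyses. Coverage of the standardised 95% CI was 94.7 to 95.0%.

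**5. Downside with useless covariates.** With hospital and three covariates, v = 1.019 and power for the standardised difference was 0.7 points below chi-square (76.5 v 77.2%). If the ten clinics (nine indicators) replaced hospital, with one covariate, v = 1.032. The formula in step 4 then gives about 75.2%, and simulation 75.0% against 76.5%: a loss of about 1 to 1.5 points.

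**The case against.** The strongest reply is that a pre-specified unadjusted comparison is legitimate, that the gain at plausible strengths is a point or so of power, and that every strength assumed here is the reviewer's choice, since H4a is a hypothesis and not evidence. All of that stands. It limits the point to an efficiency improvement and is why the result is shown as a range that includes a loss.

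It is also fair to say that the plan already reports counts and percentages by arm. A reader might infer that the report would hide the size of the MedBook effect. It would not: the difference and its CI can be computed from those counts. What is missing is a commitment to report the interval, which alone would be a minor omission.

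A reader might likewise infer that the predictors go unused. Sections 2.14 and 2.15 put them into logistic regression; they are absent only from the comparison of arms.

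Finally, covariates are not free. Ten clinics with weak covariates could cost as much power as a covariate at OR 1.5 would return. That argues for a small set, with hospital at four levels.

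**Conclusion.** The point holds as a modest, inexpensive improvement. The primary comparison is unadjusted and has no planned CI, although suitable covariates are recorded before allocation. From 76.5% power at about 309 evaluable patients, adjusting for hospital and one covariate changes power by about −0.5 to +4.7 points, with about +1 at OR 1.5. These figures rest on the planned rates, 20% loss, and assumed covariate and hospital effects.

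Two stronger readings should be resisted. A reader might infer that the chi-square test is invalid or conflicts with the z-test in 2.5. The two are the same test, and it controls type I error under randomisation. (That statement does not cover the rule "Patients readmitted to hospitals before the first review at the health clinic shall be withdrawn from the study" or the unblinded, differently timed discrepancy checks in 2.10 to 2.12, which are separate matters.) A reader might also infer that adjustment restores 80% power. That would need a covariate stronger than OR 1.8 per SD, and the documents give no basis for relying on one. The sample-size shortfall remains.

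**What to change.** In 2.15:

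- Name the primary analysis as a logistic regression of the primary outcome on arm, adjusted for hospital (four levels, not the ten clinics) and the Appendix A number of medications, optionally with age. Fix the set before any outcome data are seen.
- State whether the medication count is taken before or after corrections at discharge reconciliation, since 2.9 allows "any amendment to be documented on the discharge prescription". Both precede randomisation, so either is usable.
- Do not select covariates by the p<0.1 screen, and do not take them from Appendix B. That form records number of medications and prescriber category again at the clinic, after allocation.
- State that the test of the arm coefficient is the single deciding p-value at two-sided 0.05. Report as the effect estimate the standardised risk difference (predicted probabilities averaged over all patients under each arm) with its 95% CI.
- Keep the chi-square test and the unadjusted risk difference with 95% CI as supportive.

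If adjustment is not adopted, tie the chi-square test to the primary outcome by name and add the unadjusted risk difference with 95% CI.

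**Cost:** a few sentences, one model and no new data. About 0.5 to 1 power point is lost if the covariates are not prognostic. One extra analysis step is needed for the standardised difference and its CI; the plan does not say whether its named software provides this directly.

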### 1.5 Study Hypotheses

The study hypotheses are formulated based on the study specific objectives. For the first specific objective, the hypothesis is about the impact of MedBook Portal on the prevalence of medication discrepancies in the first prescription upon transition of care from hospitals to primary health clinics.

In terms of the second and third objectives, the hypotheses are based on the previous study conducted the hypotheses are based on the previous study conducted by Law and Chong (2017) in Malaysia. This study reported 49% of the discharge prescription were found to have a least one medication discrepancies (8).

For the fourth and fifth specific objectives, there are five variables are included as the secondary outcome of the study, namely age of patient, number of comorbidities, number of medications, type of medication (ATC categorization), and experience of prescriber (category of prescriber). All the five secondary outcomes are hypothesized to be the predictors of medication discrepancies. The hypotheses are tabulated in Table 1.1.

Table 1.1: Study Hypotheses

Specific objective 1: To assess the prevalence of medication discrepancies in the first prescription upon transition of care from hospitals to primary health clinics, comparing MedBook Portal to standard care.

H1a

There will be a significant difference of medication discrepancies rates between the intervention group and the control group after the intervention. The estimated difference of the medication discrepancies rates is 15%, with intervention group having lower medication discrepancies rates than control group.

Specific objective 2: To determine the prevalence of the type of medication discrepancies in the first prescription upon transition of care from hospitals to primary health clinics.

H2a

The prevalence of each type of medication discrepancy ranges from 5 - 60%, with Drug omission as the most common medication discrepancy in the first prescription upon transition of care from hospitals to primary health clinics.

Specific objective 3: To determine the prevalence of the type of medication discrepancies in discharge prescription.

Н3а

The prevalence of each type of medication discrepancy ranges from 5-60%, with Drug omission as the most common medication discrepancy in discharge prescription.

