# continued

Specific objective 5: To identify the predictors associated with medication discrepancies in discharge prescriptions.

H5a There is a significant association between age of patient, number of comorbidities, number of medications, type of medication (ATC categorization), experience of prescriber (category of prescriber) and medication discrepancy in discharge prescription.

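### Objectives 4 and 5 test prescriber category with ordinary logistic regression, which is too liberal if prescribers write several study prescriptions and differ in discrepancy rate

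*Combined protocol and SAP*

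**What the plan says.** Section 1.5 names five candidate predictors, and the plan commits to all of them: "All the five secondary outcomes are hypothesized to be the predictors of medication discrepancies". One is the prescriber's experience, recorded as a category. Table 1.1 links it to the clinic prescription in H4a ("experienced of prescriber (category of prescriber) and medication discrepancy in the first prescription") and to the discharge prescription in H5a ("experience of prescriber (category of prescriber) and medication discrepancy in discharge prescription").

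Section 2.15 gives the method in two steps. First: "The predictors associated with medication discrepancies will first be analysed using univariable logistic regression". Then: "The variables with p-value <0.1 by univariable analysis will be included in the multivariable logistic regression model". The threshold is common to all tests: "All statistical tests are two-tailed and p<0.05 is set to be statistically significant". Section 2.14 likewise names multiple logistic regression. No random effect, generalised estimating equation, clustered standard error or site term is mentioned.

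Section 2.7.1 lists category as the only prescriber variable to be collected. Appendix A has an item "Category of prescriber" with three options. Appendix B offers four. No readable item on either form identifies the individual prescriber.

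**The concern.** Ordinary logistic regression counts each prescription as an independent piece of evidence about category. But category belongs to the prescriber. Ten prescriptions by one medical officer are ten observations of the same person's habits, and they say less about medical officers in general than one prescription from each of ten.

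At stake is whether prescriber category is reported as a predictor of discrepancies because a few individuals happen to have high or low rates. The p<0.1 screen is exposed in the same way, since it decides which variables reach the final model.

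The timing matters. If no prescriber code is captured during data collection, the analysis cannot later be corrected at prescriber level.

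**Working it through.** **Inputs from the documents**
- Discharge prescriptions (Objective 5): 386, one per patient (section 2.5).
- First clinic prescriptions (Objective 4): 386 × (1 − 0.20) = 308.8, about 309 (20% loss, section 2.5).
- Sources: nine wards in four hospitals (Table 2.4) and ten clinics (section 2.4).
- Outcome rate: 49% (section 2.5). Two-sided 5% test and p<0.1 screen (section 2.15).

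**The plan's own figures.** 1.96² × 0.49 × 0.51 / 0.05² = 384.0, which matches the stated minimum of 384. 322 × 1.2 = 386.4, which matches the 386 recruited. No sample size or power is given for Objectives 4 and 5 themselves.

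**Will prescribers repeat?** 386 / 9 = 42.9 prescriptions per ward and 309 / 10 = 30.9 per clinic, on average. For no one to repeat, each ward would need about 43 different study prescribers and each clinic about 31. This is inference, but a strong one.

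**Assumptions.** The documents give neither the number of prescribers nor the ICC. I take 20 to 150 prescribers and ICC 0.02 to 0.10.

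**Formula.** With m prescriptions per prescriber, a predictor that is constant within prescriber has design effect DE = 1 + (m − 1) × ICC. The true error of the nominal 5% test is 2 × (1 − Φ(1.96 / √DE)).

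Example: 386 prescriptions, 40 prescribers, ICC 0.05.
- m = 386 / 40 = 9.65.
- DE = 1 + 8.65 × 0.05 = 1.43, so the correct standard error is √1.43 = 1.20 times the reported one.
- 1.96 / 1.197 = 1.637, which gives a true error of 10.2%.

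| Prescribers | 386 prescriptions, ICC 0.02 / 0.05 / 0.10 | 309 prescriptions, ICC 0.02 / 0.05 / 0.10 |
|---|---|---|
| 20 | 9.4% / 15.7% / 24.4% | 8.4% / 13.5% / 21.0% |
| 40 | 7.0% / 10.2% / 15.1% | 6.6% / 9.0% / 13.0% |
| 80 | 5.9% / 7.3% / 9.6% | 5.7% / 6.7% / 8.4% |
| 150 | 5.4% / 5.9% / 6.8% | 5.2% / 5.6% / 6.2% |

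**Check by simulation.** I assumed no true category effect, equal-sized categories and a likelihood-ratio test from ordinary logistic regression (3,000 or 4,000 runs per setting).
- When every prescription has its own prescriber, the error is 4.2% to 5.8% at every ICC, so the planned test is sound in that case.
- 386 prescriptions, 40 prescribers, ICC 0.05 / 0.10: 8.9% / 14.4% with two categories and 11.7% / 21.5% with three, the number on Appendix A.
- 386 prescriptions, 80 prescribers, three categories: 7.9% / 11.7%.
- 309 prescriptions, four categories (the number on Appendix B), ICC on the latent scale: 13.9% / 23.2% with 30 prescribers and 7.9% / 10.9% with 80.
- Screen at p<0.1, for 386 prescriptions, 40 prescribers and ICC 0.05: a null prescriber variable passes 14.6% (two categories) to 19.4% (three) of the time.

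Repeat runs and the choice of ICC scale move individual cells by up to about 3 points, so the ranges quoted elsewhere are rounded. More categories give more inflation than the formula, which treats category as a single contrast. The simulations cover the univariable test, not the full two-step procedure.

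**The case against.** The strongest reply is that the size of the problem is assumed. With 150 prescribers and ICC 0.02 the test is almost exact, and nothing in the documents excludes that. This stands, and it is why the conclusion is conditional and the range includes the benign end.

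The second reply is scope. One of five predictors in two secondary objectives is affected. Patient-level predictors such as age are much less exposed. This also stands.

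The third is cost. A prescriber code ties an individual doctor to what section 2.2.3 treats as a prescribing error, and section 2.8 takes consent from patients, not doctors. Section 2.15 also names jamovi 2.3, and the documents do not show that it can fit the models needed. Both points affect how the fix is made, not whether the standard error is right.

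A reader might infer more than the documents support:
- *That the plan considered clustering and dismissed it.* It does not discuss clustering anywhere.
- *That the primary comparison is also compromised.* Patients are randomised individually (section 2.10), so arm is not a property of the prescriber and this argument does not carry over.
- *That the forms certainly hold no identifier.* The first four items of Appendix A are not readable in the copy reviewed, so this cannot be asserted. Section 2.7.1 lists none, and the readable Appendix B items show none.
- *That a hospital or clinic fixed effect is required.* It is a debatable modelling preference, and the prescriber-level error does not depend on it.

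**Conclusion.** The concern holds conditionally. The planned model gives too small a standard error for prescriber category whenever prescribers write more than one study prescription and differ in discrepancy rate. The first condition is close to certain from the counts. The second is plausible, since the plan itself hypothesises that the prescriber matters.

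The size is not fixed by the documents. At nominal 5%, the true error is about 5.5% with 150 prescribers and ICC 0.02, about 7% to 12% with 80 prescribers and ICC 0.05 to 0.10, and about 10% to 22% with 30 to 40 prescribers at the same ICCs and two to four categories. It would be unsafe to say that the p-values are too small by any particular amount.

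This is a minor recommendation, worth acting on because the correction depends on a field captured prospectively.

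**What to change.** - **Forms.** Add a coded prescriber identifier to Appendices A and B, if they do not already hold one.
- **Section 2.15.** Fit the Objective 4 and 5 models, both the univariable screen and the multivariable model, with a prescriber random intercept or with standard errors clustered on prescriber. Name software that supports this. If prescribers turn out to be few, use a small-sample correction.
- **Reporting.** Give the number of prescribers and the number of prescriptions per prescriber in each category.
- **Leave alone.** The primary arm comparison needs no change on this account.

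The cost is one field per form, a sentence or two in section 2.15, and possibly a second package. The confidence interval for prescriber category will be wider (1.20 times on the log-odds scale in the worked example). The code must be handled confidentially, with the key kept apart from the analysis data, because it relates to doctors who are not the consented participants.

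### Screening five pre-named predictors at univariable p<0.1 can drop weak or masked ones and inflate weak ones kept; a pre-specified model, with treatment arm for the first prescription, avoids this

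*Combined protocol and SAP*

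**What the plan says.** Section 1.5 lists five candidate predictors: patient age, number of comorbidities, number of medications, ATC class of medication, and prescriber category. It adds: "All the five secondary outcomes are hypothesized to be the predictors of medication discrepancies". H4a (first clinic prescription) and H5a (discharge prescription) in Table 1.1 repeat the list.

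Section 2.14 says the predictors will be analysed by multiple logistic regression. Section 2.15 puts a univariable screen in front of it: "The variables with p-value <0.1 by univariable analysis will be included in the multivariable logistic regression model". It then applies the ordinary threshold: "All statistical tests are two-tailed and p<0.05 is set to be statistically significant". No reason for the screen is given, and nothing allows for it afterwards.

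Treatment arm is not among the five variables, and section 2.15 does not say that it enters the first-prescription model. Section 2.14 states that discharge discrepancies are measured before the intervention. The documents give no model degrees of freedom, no ATC grouping, and no expected strength or correlation of the predictors.

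**The concern.** When the hypotheses fix the variables, a data-driven screen has nothing useful to select. A predictor that fails it gets no adjusted estimate, although its hypothesis calls for one. A weak predictor that passes tends to do so in samples where its estimate is high by chance, so the reported odds ratio is too far from 1. If two correlated predictors act in opposite directions, each hides the other in univariable analysis, and the screen can remove a predictor that the joint model would have shown.

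The first-prescription model also pools two randomised groups that the trial expects to differ by 15 percentage points, without committing to a term for arm.

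At stake is the reliability of the answers to two of the five specific objectives, both secondary.

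**Working it through.** **Step 1: the plan's own figures (section 2.5).** The plan specifies "a two-tailed z-test of proportion between two groups with 80% power and a 5% of level significance will be used", with a control rate of 49% and a 15-point reduction (0.49 vs 0.34).
- Unpooled formula: n = (1.96 + 0.842)² × (0.49×0.51 + 0.34×0.66) / 0.15² = 165.45 per arm. The pooled form gives 169. The plan's 161 is within 3% of the unpooled value and gives 78.2% power; the gap does not matter here.
- Inflation: 322 × 1.2 = 386.4, matching the 386 recruited.
- Evaluable at the clinic after 20% loss: 386 × 0.8 = 308.8, about 309.

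**Step 2: does a pre-specified model fit the events?** The average rate over two equal arms is (0.49 + 0.34)/2 = 0.415. The 49% is a discharge figure; using it at the clinic is an assumption.
- Clinic events: 308.8 × 0.415 = about 128.
- Clinic df without ATC: age 1 + comorbidities 1 + medications 1 + prescriber 3 (four levels, Appendix B) + arm 1 = 7.
- With ATC at 5 df: 12 df, 128/12 = 10.7 events per parameter. With ATC at 13 df: 20 df, 128/20 = 6.4. With ATC at 5 df plus hospital (3 df): 15 df, 128/15 = 8.5.
- Discharge model: 386 × 0.49 = about 189 events. df: 1 + 1 + 1 + 2 (three prescriber levels, Appendix A) + ATC 5 = 10, so 18.9 per parameter.
- Sensitivity of the 12-df clinic model, keeping the 15-point difference: a 30% control rate gives about 69 events (69/12 = 5.8); 60% gives about 147 non-events, the smaller class (147/12 = 12.2).

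**Step 3: what screening does.** Simulation with n = 309 and 1,500 runs per setting, comparing screen-then-fit with a forced model including arm. There are five real predictors of equal strength, each entered as one term. Strengths and correlations are assumptions. Mean coefficients are log odds ratios per SD.

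| Setting | OR per SD | Dropped | True / forced / when kept | Significant: forced / screened |
|---|---|---|---|---|
| Independent | 1.2 | 54–58% | 0.18 / 0.18–0.19 / 0.28–0.29 | 32.1–36.5% / 30.7–34.3% |
| Independent | 1.3 | 31–33% | 0.26 / 0.27 / 0.32–0.33 | 58.1–59.4% / 55.5–57.0% |
| Independent | 1.5 | 8–9% | 0.41 / 0.42 / 0.42–0.43 | 88.5–90.3% / 86.8–88.3% |
| Three correlated 0.4, same direction (those three) | 1.3 | about 2% | 0.26 / 0.26–0.28 / 0.26–0.27 | 44.2–47.5% / 42.7–46.3% |
| One of the three acts in the opposite direction (that one) | 1.3 | 88% | −0.26 / −0.27 / −0.32 | 47.0% / 8.6% |
| Same | 1.5 | 84% | −0.41 / −0.42 / −0.52 | 79.8% / 14.9% |

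At OR 1.3 with independent predictors, all five survive in 14% of runs. In the masked settings, the interval of the opposite-direction predictor covers 82–83% when it is kept.

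Further simulations at n = 309 (2,000 to 3,000 runs) used real predictors correlated at most with null ones (0.4–0.5):
- OR 1.30 and 1.25 per SD were dropped 30–32% and 42–43% of the time.
- A kept OR of 1.25 averaged 1.34–1.36.
- Null predictors that survived had mean odds ratios of 1.13–1.18 and 80–90% coverage.
- Masking (OR 0.77 and 1.35, correlation 0.4) cut power from 49–52% to 23–26% and from 57–63% to 37–39%.

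**The case against.** The strongest reply is that screening seldom changes which predictors are declared. In the setting with real ORs of 1.30 and 1.25, significance was reached in 46% and 45% of runs after screening, against 48% and 45% in the forced model. Null predictors were declared in 1.6–2.0% of runs against about 5%. At n = 386 without arm, as for discharge, power was the same under both methods (59% and 58%). Outside masking, the losses in Step 3 were mostly 3 points or less and at most 5.3 (88.0% to 82.7%, an uncorrelated predictor beside three correlated ones at OR 1.5). This stands. A reader might infer that objectives 4 and 5 would report the wrong predictors; the documents and the simulations do not support that. Nothing in the documents points to opposite-direction effects, and if age, comorbidities and medications all act in the same direction, screening does little.

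Coverage among surviving nulls is conditional on selection, so setting it beside the forced model's unconditional 95% is uneven. This also stands. It shows that the intervals ignore selection, not that all of them fail.

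A reader might also infer that a full model fits the events comfortably. It does so only with a tight limit on ATC. The simulated forced models contained no ATC block, so they do not validate the whole proposal.

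Every predictor is tested univariably, and H4a and H5a speak of association. This is true, but section 2.14 promises multiple regression, and a dropped variable receives no adjusted estimate.

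Arm is randomised, so leaving it out does not confound the baseline predictors. That is correct. The reason to include it is that the trial itself expects it to shift the outcome.

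Finally, section 1.8 speaks of prioritising patients for reconciliation, but does not tie that to these models. The link is inference.

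**Conclusion.** The concern holds as a risk whose size the documents do not settle. The plan screens variables that its hypotheses already fix, uses ordinary inference afterwards, and does not commit to arm in the pooled first-prescription model. For weak predictors (assumed OR 1.25–1.30 per SD, n = 309) that are independent or correlated only with nulls, the screen drops about 30–43%, and a kept OR of 1.25 averages about 1.35. At OR 1.5, or when real predictors correlate in the same direction, the effect is small. Power loss is material only under masking.

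The forced model is feasible at about 12 df. This rests on the borrowed 49% rate, on ATC held to about 5 df, and on 10 events per parameter as a rule of thumb. Only secondary objectives 4 and 5 are affected; the primary comparison does not use the screen.

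**What to change.** In section 2.15, delete the p<0.1 rule and pre-specify one logistic model per outcome:
- Force in age, number of comorbidities, number of medications and prescriber category.
- Enter ATC as one block of about 5 df at most, with sparse groups merged and a joint likelihood-ratio test. State how a drug-level class becomes a prescription-level variable.
- Add treatment arm to the first-prescription model only, because discharge discrepancies precede the intervention.
- Use the medication count from the discharge form (Appendix A). The clinic count (Appendix B) is recorded after randomisation, and omissions or additions change it.
- Report all predictor coefficients with confidence intervals. Keep the primary comparison as the source of the treatment estimate.
- Hospital is optional; it adds 3 df.
- If events are fewer than expected, reduce the ATC terms or use penalised (Firth) estimation.

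The cost is SAP wording and slightly wider intervals than a screened model would show. No extra patients are needed, and section 2.7.1 already lists the five predictors among the data to be collected.
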